### **3.2.4 Dosage Modification**

Dose modification of rituximab is not permitted during this study. In the event of an infusion-related reaction, the rate of infusion may be adjusted (see Section 3.2.1). Patients who experience a life-threatening event, as considered by the Investigator, during an infusion of study drug should have their infusion stopped and no further infusions should be administered.

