### 3.6.5.3 Physical Examination

A physical examination will be performed by the Investigator and recorded as ‘normal’ or ‘abnormal’ with specified abnormalities at the visits indicated in Table 2. Any persisting abnormalities should be stated each time the examination is performed. Diagnosis of new abnormalities, or worsening of abnormalities, should be recorded as AEs if appropriate.

Wherever possible, the same person should perform the physical examination throughout the study (i.e., for all patients at each study center). The physical examination should include assessment of general appearance, skin, head, neck, throat, lymph nodes, thyroid, abdomen, and cardiovascular, neurological, musculoskeletal/extremities, and respiratory systems.

Body weight will also be measured. Height will be measured at Screening (Visit 1) only.

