### **6.3 Pharmacokinetic Analysis**

The PK analysis will be performed on the PK Analysis Set. The PK parameters,  $AUC_{0-t}$ ,  $AUC_{0-\infty}$ ,  $AUC_{0-d15}$ ,  $C_{max}$  after the second infusion on Day 15 and  $C_{trough}$  before the second infusion on Day 15 will be considered the primary PK endpoints. All other PK endpoints will be regarded as secondary.

The statistical analysis of the loge-transformed primary endpoints will be based on an analysis of variance model. Covariates may be added to the planned analysis. The difference in least squares means between each of the three pairs (i.e., SAIT101 vs. MabThera®, SAIT101 vs. Rituxan®, MabThera® vs. Rituxan®) and the associated 90% CI will be determined. Back transformation will provide the ratio of geometric means and 90% CI for this ratio. Equivalence will be concluded if the 90% CI for the ratio of geometric means of each of the three pairs for each primary endpoint are completely contained within the acceptance interval of 0.8 to 1.25.

Descriptive statistics (N, mean, SD, %CV, minimum, median, and maximum) will be used to summarize serum concentration data by treatment at each planned sampling time point. Concentrations that are below the lower limit of quantitation will be assigned a value of 0 for the purposes of computing descriptive statistics. Serum PK parameters calculated from the concentration-time data will also be summarized by treatment using descriptive statistics (N, mean, SD, %CV, geometric mean, geometric %CV, minimum, median, maximum).

Plots of the mean and individual serum rituximab concentrations over time for SAIT101 and MabThera® and Rituxan® will be provided following i.v. infusions.

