### 2.3. SAMPLE SIZE CALCULATION

A percentage co-efficient of variation (CV%) ranging from 26.3 to 37.3% for the five co-primary parameters is assumed for this study based on a recent study in RA patients treated with rituximab.

When the evaluable sample size in each group is 84, a three group design will have 81% power to reject both the null hypothesis that the ratio of test to standard geometrics means is below 0.800, and the null hypothesis that the ratio of test to standard geometrics means is above 1.250 (i.e., that the test and standard are not equivalent), in favor of the alternative hypothesis, that the means of the two groups are equivalent, assuming that the expected ratio of means is 1.000, the CV% for the standard is 0.330, that data will be analyzed in the log scale using analysis of variance (ANOVA) and that each one sided test is made at the 5% level. Each of the 15 hypotheses tests (five co-primary endpoints × three pairwise comparisons) are powered at 98% to 99.0% to yield 81% study-wide power.

Approximately 282 patients (94 patients per group) will be randomized in order to yield a minimum of 84 patients per group to account for a presumed 10% withdrawal.

These 94 patients in SAIT101 group and MabThera® group will provide 96% probability of declaring the equivalence in FAS with each one-sided test at the 2.5% level, accounting for a presumed 1.0 standard deviation (SD) of DAS28 from the REFLEX study, and the equivalence margin of -0.6 to 0.6 chosen as the half of a clinical meaningful improvement of 1.2 in DAS28. Considering 18% withdrawal from the REFLEX study, approximately 77 patients per group will provide approximately 91% probability of declaring the equivalence in the Per Protocol (PP) set.

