### 2.4. RANDOMIZATION

In Part A, patients will be randomized in a 1:1:1 ratio to receive the first course of SAIT101 (n=94) versus Rituxan® (n=94) versus MabThera® (n=94). The first course includes two intravenous (i.v.) 1,000 mg study drug infusions: one on Day 1 (Visit 2) and the second on Day 15 (Visit 5).

Document: \\ieedc-vnasc01\Biosdata\Archigen\SAIT101\YWA21301\Biostatistics\Documentation\SAP  
 Author: Version Number: V2.0  
 Version Date: 13Feb2019

Template No: CS\_TP\_BS016 Revision 4 Reference: CS\_WI\_BS005  
 Effective Date: 01Apr2016

In Part B, eligible patients in the SAIT101 arm or MabThera® arm will receive the second course of SAIT101 treatment or MabThera®, respectively, at Week 24 and Week 26, however, in the Rituxan® arm will be randomized in a 1:1 ratio to receive SAIT101 or Rituxan® treatment at Weeks 24 and 26. The second course includes two 1,000 mg i.v. infusions (one at Week 24 and the second infusion at Week 26 [14 days later]) of study drug.

At Week 24, patients will be evaluated for further course of the infusion, i.e. Part B.

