### Demographics

- Age (years) – calculated to date of Informed Consent
- Age group – 18-60 years, >60 years
- Gender – Female, Male
- Ethnicity– Hispanic or Latino, Not Hispanic or Latino, Not Reported, Unknown
- Race – American Indian or Alaska Native, Asian, Black or African American, Native Hawaiian or other Pacific Islander, White, Other, Unknown, Not Reported
- Weight (kg) at Baseline
- Height (cm) at Baseline
- BMI (kg/m^2) at Baseline – derived as weight (kg)/(height (m))

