$t_{1/2}$ , Interval	The time interval (h) of the log-linear regression to determine $\lambda_z$ .
$t_{1/2}$ , N	Number of data points included in the log-linear regression analysis to determine $\lambda_z$ . A minimum of 3 data points will be used for determination.
$R_{sq}$	Goodness-of-fit statistic for calculation of $\lambda_z$ (Regression coefficient).
%AUC ex	Percentage of $AUC_{(0-\text{inf})}$ obtained by extrapolation, calculated as $[(C_{\text{last}}/\lambda_z)/AUC_{(0-\text{inf})} \times 100]$ .

The following criteria will be assessed:

- if  $AUC_{(0-t)}$  is less than 80.0% of  $AUC_{(0-\infty)}$  (i.e. %AUCex>20.0%), the data will be flagged in the listing.
- if predose concentration is greater than 5% of  $C_{\max, \text{dose1}}$  for a subject, the concentration data and parameters for this subject will be flagged in the listing and excluded from summary statistics.

For partial areas from interval time 1 ( $t_1$ ) to time 2 ( $t_2$ ), if  $t_2$  is missing,  $AUC_{(t_1-t_2)}$  will not be calculated.

Pharmacokinetic parameters will be listed and summarized by treatment using descriptive statistics (n, mean, SD, CV%, minimum, median, maximum, geometric mean, and geometric CV%, except that  $t_{\max}$  will be reported with n, minimum, median, and maximum only).

The additional following summaries of PK parameters will be generated:

- By treatment and region (US, EU, Other)
- By treatment and age category (18-60 years and >60 years)
- By treatment and sex
- By treatment and ADA status at baseline.

The PK parameters,  $AUC_{(0-t)}$ ,  $AUC_{(0-\text{inf})}$ ,  $AUC_{(0-d15)}$ ,  $C_{\max, \text{dose2}}$  after the second infusion on Day 15, and  $C_{\text{trough}}$ , before the second infusion on Day 15 will be considered the co-primary PK endpoints. All other PK endpoints will be regarded as secondary.

A statistical comparison of the loge-transformed primary parameters between treatments will be based on an analysis of variance model. No covariates will be included. The difference in least squares means between the

Document: \\ieedc-vnasc01\Biosdata\Archigen\SAIT101\YWA21301\Biostatistics\Documentation\SAP	
Author:	Version Number: V2.0
	Version Date: 13Feb2019

Template No: CS_TP_BS016 Revision 4	Reference: CS_WI_BS005
Effective Date: 01Apr2016	

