test (SAIT101) and the reference (MabThera® or Rituxan®) treatments and the associated 90% CI will be calculated. Comparison between the reference treatments will also be performed. Back transformation will provide the ratio of geometric means between treatments and 90% CI for this ratio. Equivalence will be concluded if the 90% CI for the ratio of geometric means of test/reference for primary endpoints are completely contained within the acceptance interval of 0.80 to 1.25. Least-squares geometric means will be also presented for each treatment with corresponding 95% CIs. BLQ values for  $C_{trough}$  will be treated as LOQ/2 for all statistical comparison. Line plots will be generated to visually display all comparisons for all primary parameters.

A sensitivity analysis will be performed for the above comparisons, in which the above comparison will be replicated, with the addition of the following covariates to the statistical model: Age, sex, ADA status at baseline, body weight at baseline.

An exploratory statistical assessment of the impact of baseline ADA status (Positive or Negative) will be completed by adding this fixed effect to the model used in the primary statistical analysis. The ratio of geometric means for ADA positive/ADA negative will be reported with the 90% CI for this ratio.

Scatter plots of individual and geometric mean PK parameters  $AUC_{(0-inf)}$ ,  $AUC_{(0-t)}$ ,  $AUC_{(0-d15)}$ ,  $C_{max,dose2}$  after the second infusion on Day 15 and  $C_{trough}$  before the second infusion on Day 15 versus treatment will be presented. Additional, graphical presentations of PK data may be added at the discretion of the PK scientist, if further illustration of the PK results is deemed appropriate.

Additional impact analyses will be performed to evaluate the impact of site 10703 on the primary analysis, and the statistical significance of any PK differences associated with this site. The first impact analysis will entail repeating the primary analysis above but excluding site 10703. The second impact analysis will entail adding two fixed effects to the primary model: Site1073 (Yes/No), Site10703 x Treatment interaction, and testing both effects at the two-sided 5% significance level. The type 3 p-values will be reported for all effects in this model, but no treatment or site comparison estimates will be made.

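### The deciding PK model leaves out baseline body weight although dosing is flat, weight is already recorded and covariates are permitted, so available precision goes unused

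*SAP*

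**What the plan says.** - **Deciding model.** SAP 13.2 compares the log-transformed co-primary parameters by ANOVA and states "No covariates will be included". The 0.80 to 1.25 rule is applied to the 90% intervals from this model.
- **Sensitivity model.** The same section repeats the comparisons "with the addition of the following covariates to the statistical model: Age, sex, ADA status at baseline, body weight at baseline". No equivalence decision is attached to that result.
- **Protocol.** Section 6.3 leaves the option open: "Covariates may be added to the planned analysis". It names none.
- **Dose.** SAP 2.4: "The first course includes two intravenous (i.v.) 1,000 mg study drug infusions". Protocol 3.2.4: "Dose modification of rituximab is not permitted during this study". Exposure is not scaled to body size.
- **Weight data.** Protocol 3.6.5.3: "Body weight will also be measured". SAP section 9 lists "Weight (kg) at Baseline" among the demographics.
- **Allocation.** Protocol 3.5.2 describes a 1:1:1 study-level scheme and mentions no stratification factor.

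**The concern.** With a flat dose, any dependence of exposure on body size stays in the between-patient variance. An unadjusted model puts that variance in the error term, where it widens every interval. A linear adjustment for one baseline measurement would remove it at almost no cost.

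The stakes are high because the success rule is conjunctive. Protocol 6.3 requires all three pairs on each of five endpoints to fall within the limits, which makes 15 tests. A small loss of precision per test accumulates. If the unadjusted interval for one endpoint just crosses a limit and the weight-adjusted interval does not, the plan gives the adjusted result no role in the decision.

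The SAP handles its other main comparisons differently. The DAS28-CRP analysis (15.1.3) adjusts for baseline DAS28-CRP, and the CD19+ AUEC analysis (14.2) adjusts for the baseline CD19+ value. The analysis serving the primary objective is the one left unadjusted.

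**Working it through.** **Inputs from the documents.** 84 evaluable patients per group, three groups, true ratio 1.000, CV 0.330, cited CV range 26.3 to 37.3%, 15 tests at 98 to 99% each, study-wide power 81% (SAP 2.3); "each one sided test is made at the 5% level"; limits 0.80 to 1.25 (SAP 13.2).

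**Assumed input.** R², the share of log-PK variance explained by weight, is not in the documents. It is set to 5, 10, 20 and 30%, the same for all endpoints.

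**Formulas**
- Log SD = √ln(1 + CV²).
- SE of a pairwise difference = SD × √(2/84).
- Error df = 3 × 84 − 3 = 249 unadjusted, 248 with one covariate.
- Per-test power p = probability that the 90% interval lies within ±ln 1.25 = ±0.2231.
- Study-wide power = p¹⁵, treating the tests as independent.
- Adjustment multiplies the SD by √(1 − R²).

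**Step 1: the plan's own figure.** At CV 0.330 the log SD is √ln(1.1089) = 0.3215 and the SE is 0.3215 × 0.1543 = 0.0496. The 90% half-width is about 0.082. Exact two-one-sided-tests power is p = 0.9955, and 0.9955¹⁵ = 0.93. The stated 81% is not reproduced. It needs p = 0.81^(1/15) = 0.986, which corresponds to a CV of about 0.362, a value the documents do not state. The stated 98 to 99% per test gives 0.98¹⁵ = 0.74 to 0.99¹⁵ = 0.86, which brackets 81%. A product calculation is therefore plausible, but the plan does not say that one was used.

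**Step 2: effect of weight on precision**

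| Assumed R² | SE multiplier √(1 − R²) | SE reduction | Equivalent n per group, 84/(1 − R²) |
|---|---|---|---|
| 5% | 0.975 | 2.5% | 88 |
| 10% | 0.949 | 5% | 93 |
| 20% | 0.894 | 11% | 105 |
| 30% | 0.837 | 16% | 120 |

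**Step 3: study-wide power, true ratio 1.0, 15 independent tests**

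| CV on all five endpoints | No covariate | R² 5% | 10% | 20% | 30% |
|---|---|---|---|---|---|
| 0.330 (stated) | 93% | 95% | 97% | 99% | 99.7% |
| 0.373 (top of cited range) | 75% | 81% | 86% | 93% | 97% |

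**Step 4: correlated tests.** The three pairs share arms, and the five endpoints come from one concentration profile. Joint power was simulated with an assumed common endpoint correlation of 0.5 to 0.8, which is not in the documents. At CV 0.330 the unadjusted figure is 95 to 96%, rising to 97 to 98% at R² = 10%. At CV 0.373 it is 81 to 87%, rising to 89 to 92%. The start is higher and the gain smaller than in Step 3.

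**Step 5: true ratio off 1.** Assume a ratio of 0.95 for the ten SAIT101 comparisons and 1.00 for the five between the reference products, at CV 0.330 with independent tests. Power goes from about 68% to 78% at R² = 10% and 87% at 20%.

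**The case against.** The unadjusted ANOVA is valid after 1:1:1 randomisation. It is the model assumed for the sample size, and the protocol makes covariates optional. The SAP closes that option in advance and already commits to reporting weight-adjusted comparisons. The documents give no relation between weight and rituximab PK: Protocol 1.3.1 summarises clearance and volume of distribution without mentioning weight. If R² is near zero, nothing is gained.

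All of this stands as fact. It fixes the point as one of efficiency and makes the size conditional on an assumption. It does not remove the point. The sensitivity model cannot change the equivalence conclusion, and by adding four covariates together it does not isolate weight.

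Three stronger readings are tempting and unsupported.
- **Power would rise from 81% to 86, 90, 95 or 98%.** That starts from the back-solved CV of about 0.362. At the stated CV of 0.330, power is already about 93%. The mismatch between 81% and 0.330 is a separate matter to reconcile.
- **Chance weight imbalance biases the ratios.** Under randomisation it is not bias. It is already part of the unadjusted standard error, so counting it again repeats the variance argument.
- **The SAP itself makes all 15 intervals decisive.** Protocol 6.3 does. SAP 13.2 attaches the acceptance limits to test versus reference and says only that the references will also be compared. With ten tests, unadjusted power at CV 0.330 is 0.9955¹⁰ ≈ 96%, which leaves less to gain.

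**Conclusion.** The point holds as a missed efficiency gain. The deciding PK model omits a baseline variable that is already collected and that the sponsor itself considers worth adjusting for. A reader might infer that weight is ignored or that the primary analysis is invalid. Neither is so: weight is in a pre-specified sensitivity model, and the unadjusted comparison is sound.

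At the stated CV and a true ratio of 1.0 the gain is modest: about 2 to 4 points of study-wide power for R² of 5 to 10%, from a start of 93%. It is larger where the plan is more exposed: about 6 to 11 points for the same R² if all five endpoints had a CV of 37.3%, or about 10 points at R² = 10% in the Step 5 scenario. These figures rest on an assumed R² common to all endpoints, 84 evaluable patients per group for every endpoint, and independent tests. Correlation shrinks the gain without reversing it. On the log scale with a linear model, the adjusted and unadjusted contrasts target the same geometric mean ratio, so the margin and alpha are unchanged.

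**What to change.** Before unblinding, amend SAP 13.2 so that the deciding model is log(parameter) = treatment + log(baseline body weight), with the 0.80 to 1.25 rule applied to its 90% intervals. Keep the unadjusted ANOVA as the sensitivity analysis, and record the change in SAP 2.6. Protocol 6.3 already permits covariates, and the planned sensitivity analysis already needs weight in the analysis data, so no new data are required.

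The cost is SAP wording, one of 249 error degrees of freedom, and presenting unadjusted ratios beside the adjusted ones.

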
The PK analysis will be performed on the PK Analysis Set. The PK parameters, <math>AUC_{0-t}</math>, <math>AUC_{0-\infty}</math>, <math>AUC_{0-d15}</math>, <math>C_{max}</math> after the second infusion on Day 15 and <math>C_{trough}</math> before the second infusion on Day 15 will be considered the co-primary PK endpoints. All other PK endpoints will be regarded as secondary.
 
The statistical analysis of the <math>\log_e</math>-transformed primary endpoints will be based on an analysis of variance model. The difference in least squares means between each of the three pairs (SAIT101 vs. MabThera®, SAIT101 vs. Rituxan®, and MabThera® vs. Rituxan®) and the associated 90% confidence interval (CI) will be determined. Back transformation will provide the ratio of geometric means and 90% CI for this ratio. Equivalence will be concluded if the 90% CI for the ratio of geometric means of each of the three pairs for primary endpoints are completely contained within the acceptance interval of 0.8 to 1.25.
 
Descriptive statistics (N, mean, standard deviation, coefficient of variation (CV), minimum, median, and maximum) will be used to summarize serum concentration data by treatment at each planned sampling time point. Concentrations that are below the lower limit of quantification will be assigned a value of 0 for the purposes of computing descriptive statistics. Serum PK parameters calculated from the concentration-time data will also be summarized by treatment using descriptive statistics.
 
Plots of the mean and individual serum rituximab concentrations over time for SAIT101 and MabThera® or Rituxan® will be provided following i.v. infusions.
 
Pharmacodynamic Analyses
 
Observed, change from Baseline, and percent change from Baseline in CD19+ B cell counts, depletion incidence for CD19+ B cell counts, time needed to B cell depletion, duration of CD19+ B cell depletion and IgG, IgM, IgA, CRP levels will be summarized using descriptive statistics.
 
Efficacy Analyses
 
The change from Baseline in DAS28 at Week 24 will be considered the main efficacy endpoint.
 
Two-sided 95% CI for the difference between SAIT101 and MabThera® in DAS28 change from Baseline at Week 24 will be computed from an analysis of covariance using Baseline DAS28 as covariate and treatment as model factors. Equivalence will be concluded if the 95% CI for the mean difference for main endpoint is completely contained with the equivalence margin of -0.6 to 0.6. Both of the per protocol (PP) set and full analysis set (FAS) will be considered as the efficacy analysis population and no missing data will be imputed for the efficacy analyses in FAS.
 
Continuous variables will be summarized using N, mean, standard deviation, minimum, median, and maximum. Categorical variables will be summarized using frequency counts and percentages.
 
Safety Analyses
 
All reported terms for AEs will be coded using the Medical Dictionary for Regulatory Activities (MedDRA). No statistical testing will be performed for AEs. For all AE and SAE tables, patients will be counted at most once for each Preferred Term (PT) and each System Organ Class (SOC). Adverse events will be summarized by the number and percentage of patients experiencing events by SOC, PT and severity.
 
Changes in vital signs and clinical laboratory measurements will be summarized descriptively by visit. Other safety variables will be summarized and listed.
 
Immunogenicity Analyses
 
Incidence of HACA and neutralizing antibody and summary of counts of antibodies per patient at prior first dose on Day 1 and at Week 1, 2, 4, 12, 16, 24, 36 and 52 will be summarized overall and by treatment group.
 
Interim Analysis
 
Interim Analyses of 10 patients per group (30 patients in total) of safety data collected up to Week 4 and 20 patients per group (60 patients in total) of safety data collected up to Week 12 are planned.
		

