## 2.6. CHANGES TO ANALYSIS FROM PROTOCOL

Summary for Change from Baseline in DAS28-ESR at Week 8, 16, 24, 36 and 52 will be added. Comparison between SAIT101 and Rituxan® will be added as exploratory analyses in [section 15.2.5](#).

Definition of depletion in CD19+ B cell count was updated from CD19+ B cell count below 14/ $\mu$ L to CD19+ B cell count below 20/ $\mu$ L, because the assay limit reported by the central laboratory is 20 cells/ $\mu$ L.

To evaluate differences among Mexican site 10703 and all other sites between baseline characteristics, additional tables of baseline characteristics will be added by site 10703 vs other sites in [section 9](#).

Two additional impact analyses will be added for PK in [section 13.2](#) and one will be added for main efficacy analysis in [section 15.2.7](#).

The study will be unblinded until Week 52, instead of Week 24 in protocol, per sponsor decision.

There will be no interim analysis and CSR prepared based on the 24-week data of all patients. Analysis of Part A and Part B will be combined into one final analysis.

Additional analyses for immunogenicity have been added in [section 17](#), per sponsor decision.

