### 3.2. FINAL ANALYSIS (W52 CSR)

The analysis of primary, secondary and exploratory endpoints, including PK/PD, efficacy, safety and

---

Document:	\\eedc-vnasc01\Biosdata\Archigen\SAIT101\YWA21301\Biostatistics\Documentation\SAP		
Author:		Version Number:	V2.0
		Version Date:	13Feb2019

Template No: CS\_TP\_BS016 Revision 4  
Effective Date: 01Apr2016

Reference: CS\_WI\_BS005

immunogenicity, will be performed per protocol based on procedures outlined in this SAP based on the 52-week data of all patients.

The study will be unblinded only at Week 52 and a Week 52 CSR (W52 CSR) will be prepared based on the 52-week data of all patients.

The analysis for W52 CSR will be performed by IQVIA Biostatistics following sponsor authorization of this Statistical Analysis Plan, database lock and sponsor authorization of analysis sets.

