## 6.2. MULTIPLE COMPARISON/MULTIPLICITY

No multiple comparison adjustment will be used for main efficacy analysis, since there is only one main efficacy analysis for change from baseline at Week 24. No multiple comparison adjustment will be used either for the PK analyses since the significance level is pre-specified at 10% (two-sided) to show equivalence within pre-specified limits, and the overall power for the PK equivalence assessment accounts for the multiple testing.

---

Document: \\ieedc-vnasc01\Biosdata\Archigen\SAIT101\YWA21301\Biostatistics\Documentation\SAP  
Author: Version Number: V2.0

Version Date: 13Feb2019

Template No: CS\_TP\_BS016 Revision 4  
Effective Date: 01Apr2016

Reference: CS\_WI\_BS005

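### The SAP's PK success rule covers only the SAIT101/reference ratios, whereas the protocol requires all three pairs to pass

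*SAP*

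**What the plan says.** Protocol 6.3 names three pairs (SAIT101 vs MabThera, SAIT101 vs Rituxan, MabThera vs Rituxan) and sets the rule: "Equivalence will be concluded if the 90% CI for the ratio of geometric means of each of the three pairs for each primary endpoint" lies inside 0.8 to 1.25. The synopsis, under Pharmacokinetic Analyses, has the same rule: "Equivalence will be concluded if the 90% CI for the ratio of geometric means of each of the three pairs for primary endpoints". With five co-primary endpoints, that is 15 intervals.

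SAP 13.2 identifies test with SAIT101 and reference with MabThera or Rituxan. It then adds "Comparison between the reference treatments will also be performed" and sets its criterion: "Equivalence will be concluded if the 90% CI for the ratio of geometric means of test/reference for primary endpoints are completely contained" within 0.80 to 1.25. It gives no criterion for MabThera vs Rituxan.

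Other parts of the SAP bear on this:

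- Section 2.3: "Each of the 15 hypotheses tests (five co-primary endpoints × three pairwise comparisons) are powered at 98% to 99.0% to yield 81% study-wide power".
- Section 6.2 gives as one reason for making no multiplicity adjustment that "the overall power for the PK equivalence assessment accounts for the multiple testing".
- Section 2.6 lists departures from the protocol. Its only PK entry concerns one site: "Two additional impact analyses will be added for PK in" section 13.2.
- Section 3.2 says the final analysis "will be performed per protocol based on procedures outlined in this SAP".

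**The concern.** This is the success criterion for the primary objective, and the two governing documents word it differently. Under SAP 13.2's own definitions, MabThera/Rituxan is not a test/reference ratio. Read literally, that comparison is calculated and reported but cannot block a conclusion of equivalence. The word *or* in the definition of reference also leaves unsaid that SAIT101 must pass against both products.

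The 10 SAP intervals are a subset of the 15 protocol intervals, so the conflict runs one way. If both SAIT101 comparisons pass and one MabThera/Rituxan interval does not, the SAP concludes equivalence and the protocol does not. Someone would then have to choose the rule with the results in view, which pre-specification is meant to prevent.

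**Working it through.** **1. Counting intervals.** Protocol: 5 endpoints × 3 pairs = 15. SAP 13.2 read literally: 5 × 2 = 10. SAP 2.3: 15.

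**2. The plan's own power figure.** Over 15 independent tests, 0.98^15 = 73.9%, 0.986^15 = 80.9% and 0.99^15 = 86.0%. The stated 81% therefore fits a 15-test rule at about 98.6% per test. Ten tests at 98.6% give 0.986^10 = 86.8%, so the stated figure belongs to the three-pair rule.

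The 81% does not follow from the stated CV of 0.330. With n = 84, ratio 1.000 and one-sided 5%, power is 99.5% per test and 93.3% over 15 independent tests. Power of 98.6% per test needs a CV of about 36.2%. That is a separate matter, and nothing below depends on it.

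**3. A single case where the rules disagree.** Inputs from SAP 2.3: n = 84 per arm, CV 33%.

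- Log-scale SD = √ln(1 + 0.33²) = 0.3215
- SE of a difference = 0.3215 × √(2/84) = 0.0496
- t(0.95, 249 df) = 1.651, so the 90% CI half-width is 1.651 × 0.0496 = 0.0819 on the log scale

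| Pair | Ratio (90% CI) | Within 0.80–1.25? |
|---|---|---|
| SAIT101/MabThera | 0.909 (0.838–0.987) | yes |
| SAIT101/Rituxan | 1.10 (1.014–1.194) | yes |
| MabThera/Rituxan | 1.10/0.909 = 1.21 (1.115–1.313) | no |

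The literal SAP rule passes this result and the protocol rule fails it.

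**4. How often the rules would disagree.** Simulation of 200,000 trials per setting: three arms of 84, CV 33% for every endpoint, pooled variance with 249 df, and five endpoints with common correlation 0 / 0.5 / 0.8. The correlations, the true MabThera/Rituxan ratio and SAIT101's position are assumptions; the documents give none of them, except that the power calculation takes the ratio as 1.000. The true shift applies to all five endpoints at once. SAIT101 is midway between the references on the log scale.

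| True MabThera/Rituxan | SAP rule passes, % | Protocol rule passes, % | SAP passes and protocol fails, % |
|---|---|---|---|
| 1.00 | 95.8 / 96.2 / 97.3 | 94.0 / 94.7 / 96.1 | 1.8 / 1.5 / 1.1 |
| 1.05 | 90.7 / 92.2 / 94.5 | 79.0 / 84.0 / 88.7 | 12 / 8 / 6 |
| 1.10 | 73.5 / 78.9 / 85.1 | 32.3 / 49.9 / 62.1 | 41 / 29 / 23 |
| 1.15 | 44.1 / 55.4 / 67.5 | 2.8 / 15.2 / 27.4 | 41 / 40 / 40 |

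Variations on the last column:

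- SAIT101 equal to one reference: 10 / 7 / 5% at 1.05, 18 / 17 / 15% at 1.10, 3 / 10 / 14% at 1.15.
- References differ on one endpoint only, SAIT101 midway: 3 to 4% at 1.05, about 15% at 1.10, about 36% at 1.15.
- Mixed CVs from 26.3% to 37.3% (end points from SAP 2.3, intermediate values assumed), SAIT101 midway, all endpoints shifted: 2.3 / 2.1 / 1.7% at 1.00, 11 / 8 / 6% at 1.05, 38 / 27 / 22% at 1.10, 43 / 39 / 37% at 1.15.

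**The case against.** The best reply is that this is loose drafting and the SAP means the protocol's rule. It never says the SAIT101 ratios alone decide. Section 2.3 counts 15 tests, section 3.2 defers to the protocol, section 2.6 declares no change, and section 13.2 calculates and plots the third comparison. The sample-size text also uses two-arm test-versus-standard language while counting MabThera vs Rituxan, so test/reference could be similar shorthand. All 15 intervals will be reported, so the protocol rule can be applied to the SAP's output. The documents describe the two references as brand names of one product, which makes a true difference of 10% or more a strong assumption.

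Much of this is fair. The documents do not show whether the wording is deliberate. No error rate is inflated for either SAIT101 comparison: when every interval must pass, no alpha adjustment is needed for 10 tests or 15, and power under 10 tests would be higher than stated. Section 6.2 therefore shows the internal inconsistency but no type I error problem. The larger percentages depend on assumed reference differences, mostly on all endpoints together.

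The conflict remains. Section 13.2 ties test explicitly to SAIT101 just before stating its rule, and it is the section that sets the criterion. Reporting the third interval does not settle whether its failure blocks the conclusion.

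**Conclusion.** The point holds: the rule in SAP 13.2 is wrong as written against protocol 6.3 and the synopsis, and inconsistent with the 15-test basis in SAP 2.3. It must be fixed because it is the primary decision rule, not because disagreement is likely. Under the plan's own assumption of equal products, the two rules part in under 2% of trials at CV 33%, and in about 2% with the mixed CVs. Disagreement becomes material only if the references truly differ by roughly 5% or more: 6 to 12% of trials at a ratio of 1.05 and 23 to 41% at 1.10, with SAIT101 midway and all five endpoints shifted. It is less if only one endpoint differs or SAIT101 matches one reference. The textual finding depends on none of these assumptions.

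**What to change.** Before unblinding, replace the criterion in SAP 13.2 with wording such as: *PK equivalence is declared only if the 90% CIs for all three pairs (SAIT101/MabThera, SAIT101/Rituxan, MabThera/Rituxan) lie within 0.80 to 1.25 on every one of the five co-primary endpoints.* This costs one sentence. It needs no protocol amendment and no new data, since the third comparison is already planned.

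If a two-pair rule is what the sponsor wants, declare and justify it in SAP 2.6, state that SAIT101 must pass against both references, and redo the power statement for 10 tests in SAP 2.3, protocol 6.1 and the synopsis. That costs more, because it departs from the rule in protocol 6.3 and the synopsis.

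The documents do not show whether unblinding has already taken place. If it has, the report should apply the protocol's three-pair rule and disclose the discrepancy in the SAP.
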